11.1.3 Methods for Evaluation of Measurable Disease

All measurements should be taken and recorded in metric notation using a ruler or calipers. All baseline evaluations should be performed as closely as possible to the beginning of treatment and never more than 4 weeks before the beginning of the treatment.

The same method of assessment and the same technique should be used to

characterize each identified and reported lesion at baseline and during follow-up. Imaging-based evaluation is preferred to evaluation by clinical examination unless the lesion(s) being followed cannot be imaged but are assessable by clinical exam.

Clinical lesions Clinical lesions will only be considered measurable when they are superficial (*e.g.*, skin nodules and palpable lymph nodes) and ≥ 10 mm diameter as assessed using calipers (*e.g.*, skin nodules). In the case of skin lesions, documentation by color photography, including a ruler to estimate the size of the lesion, is recommended.

Chest x-ray Lesions on chest x-ray are acceptable as measurable lesions when they are clearly defined and surrounded by aerated lung. However, CT is preferable.

Conventional CT and MRI This guideline has defined measurability of lesions on CT scan based on the assumption that CT slice thickness is 5 mm or less. If CT scans have slice thickness greater than 5 mm, the minimum size for a measurable lesion should be twice the slice thickness. MRI is also acceptable in certain situations (*e.g.* for body scans).

Use of MRI remains a complex issue. MRI has excellent contrast, spatial, and temporal resolution; however, there are many image acquisition variables involved in MRI, which greatly impact image quality, lesion conspicuity, and measurement. Furthermore, the availability of MRI is variable globally. As with CT, if an MRI is performed, the technical specifications of the scanning sequences used should be optimized for the evaluation of the type and site of disease. Furthermore, as with CT, the modality used at follow-up should be the same as was used at baseline and the lesions should be measured/assessed on the same pulse sequence. It is beyond the scope of the RECIST guidelines to prescribe specific MRI pulse sequence parameters for all scanners, body parts, and diseases. Ideally, the same type of scanner should be used and the image acquisition protocol should be followed as closely as possible to prior scans. Body scans should be performed with breath-hold scanning techniques, if possible.

PET-CT At present, the low dose or attenuation correction CT portion of a combined PET-CT is not always of optimal diagnostic CT quality for use with RECIST measurements. However, if the site can document that the CT performed as part of a PET-CT is of identical diagnostic quality to a diagnostic CT (with IV and oral contrast), then the CT portion of the PET-CT can be used for RECIST measurements and can be used interchangeably with conventional CT in accurately measuring cancer lesions over time. Note, however, that the PET portion of the CT introduces additional data which may bias an investigator if it is not routinely or serially performed.

Ultrasound Ultrasound is not useful in assessment of lesion size and should not

be used as a method of measurement. Ultrasound examinations cannot be reproduced in their entirety for independent review at a later date and, because they are operator dependent, it cannot be guaranteed that the same technique and measurements will be taken from one assessment to the next. If new lesions are identified by ultrasound in the course of the study, confirmation by CT or MRI is advised. If there is concern about radiation exposure at CT, MRI may be used instead of CT in selected instances.

Endoscopy, Laparoscopy The utilization of these techniques for objective tumor evaluation is not advised. However, such techniques may be useful to confirm complete pathological response when biopsies are obtained or to determine relapse in trials where recurrence following complete response (CR) or surgical resection is an endpoint.

Tumor markers Tumor markers alone cannot be used to assess response. If markers are initially above the upper normal limit, they must normalize for a patient to be considered in complete clinical response.

Cytology, Histology These techniques can be used to differentiate between partial responses (PR) and complete responses (CR) in rare cases (*e.g.*, residual lesions in tumor types, such as germ cell tumors, where known residual benign tumors can remain).

The cytological confirmation of the neoplastic origin of any effusion that appears or worsens during treatment when the measurable tumor has met criteria for response or stable disease is mandatory to differentiate between response or stable disease (an effusion may be a side effect of the treatment) and progressive disease.

FDG-PET While FDG-PET response assessments need additional study, it is sometimes reasonable to incorporate the use of FDG-PET scanning to complement CT scanning in assessment of progression (particularly possible 'new' disease). New lesions on the basis of FDG-PET imaging can be identified according to the following algorithm:

- a. Negative FDG-PET at baseline, with a positive FDG-PET at follow-up is a sign of PD based on a new lesion.
- b. No FDG-PET at baseline and a positive FDG-PET at follow-up: If the positive FDG-PET at follow-up corresponds to a new site of disease confirmed by CT, this is PD. If the positive FDG-PET at follow-up is not confirmed as a new site of disease on CT, additional follow-up CT scans are needed to determine if there is truly progression occurring at that site (if so, the date of PD will be the date of the initial abnormal FDG-PET scan). If the positive FDG-PET at follow-up corresponds to a pre-existing site of disease on CT that is not progressing on the basis of the anatomic images, this is not PD.
- c. FDG-PET may be used to upgrade a response to a CR in a manner similar to a biopsy in cases where a residual radiographic abnormality is thought

to represent fibrosis or scarring. The use of FDG-PET in this circumstance should be prospectively described in the protocol and supported by disease-specific medical literature for the indication. However, it must be acknowledged that both approaches may lead to false positive CR due to limitations of FDG-PET and biopsy resolution/sensitivity.

Note: A 'positive' FDG-PET scan lesion means one which is FDG avid with an uptake greater than twice that of the surrounding tissue on the attenuation corrected image.

11.1.4 Response Criteria

11.1.4.1 Evaluation of Target Lesions

Complete Response (CR): Disappearance of all target lesions. Any pathological lymph nodes (whether target or non-target) must have reduction in short axis to <10 mm.

Partial Response (PR): At least a 30% decrease in the sum of the diameters of target lesions, taking as reference the baseline sum diameters.

Progressive Disease (PD): At least a 20% increase in the sum of the diameters of target lesions, taking as reference the smallest sum on study (this includes the baseline sum if that is the smallest on study). In addition to the relative increase of 20%, the sum must also demonstrate an absolute increase of at least 5 mm. (Note: the appearance of one or more new lesions is also considered progressions).

Stable Disease (SD): Neither sufficient shrinkage to qualify for PR nor sufficient increase to qualify for PD, taking as reference the smallest sum diameters while on study.

11.1.4.2 Evaluation of Non-Target Lesions

Complete Response (CR): Disappearance of all non-target lesions and normalization of tumor marker level. All lymph nodes must be non-pathological in size (<10 mm short axis).

Note: If tumor markers are initially above the upper normal limit, they must normalize for a patient to be considered in complete clinical response.

Non-CR/Non-PD: Persistence of one or more non-target lesion(s) and/or maintenance of tumor marker level above the normal limits.

Progressive Disease (PD): Appearance of one or more new lesions and/or *unequivocal progression* of existing non-target lesions. *Unequivocal progression* should not normally trump target lesion status. It must be representative of overall disease status change, not a single lesion increase.

Although a clear progression of “non-target” lesions only is exceptional, the opinion of the treating physician should prevail in such circumstances, and the progression status should be confirmed at a later time by the review panel (or Principal Investigator).

11.1.4.3 **Evaluation of Best Overall Response**

The best overall response is the best response recorded from the start of the treatment until disease progression/recurrence (taking as reference for progressive disease the smallest measurements recorded since the treatment started). The patient's best response assignment will depend on the achievement of both measurement and confirmation criteria.

For Patients with Measurable Disease (i.e., Target Disease)

Target Lesions	Non-Target Lesions	New Lesions	Overall Response	Best Overall Response when Confirmation is Required*
CR	CR	No	CR	≥4 wks. Confirmation**
CR	Non-CR/Non-PD	No	PR	≥4 wks. Confirmation**
CR	Not evaluated	No	PR	
PR	Non-	No	PR	

	CR/Non-PD/not evaluated			
SD	Non-CR/Non-PD/not evaluated	No	SD	Documented at least once ≥ 4 wks. from baseline**
PD	Any	Yes or No	PD	no prior SD, PR or CR
Any	PD***	Yes or No	PD	
Any	Any	Yes	PD	

* See RECIST 1.1 manuscript for further details on what is evidence of a new lesion.
 
** Only for non-randomized trials with response as primary endpoint.
 
*** In exceptional circumstances, unequivocal progression in non-target lesions may be accepted as disease progression.
 
Note: Patients with a global deterioration of health status requiring discontinuation of treatment without objective evidence of disease progression at that time should be reported as “symptomatic deterioration.” Every effort should be made to document the objective progression even after discontinuation of treatment.
				

For Patients with Non-Measurable Disease (*i.e.*, Non-Target Disease)

Non-Target Lesions	New Lesions	Overall Response
CR	No	CR
Non-CR/non-PD	No	Non-CR/non-PD*
Not all evaluated	No	not evaluated
Unequivocal PD	Yes or No	PD
Any	Yes	PD

* ‘Non-CR/non-PD’ is preferred over ‘stable disease’ for non-target disease since SD is increasingly used as an endpoint for assessment of efficacy in some trials so to assign this category when no lesions can be measured is not advised
		

11.1.5 Duration of Response

Duration of overall response: The duration of overall response is measured from the time measurement criteria are met for CR or PR (whichever is first recorded) until the first date that recurrent or progressive disease is objectively documented (taking as reference for progressive disease the smallest measurements recorded since the treatment started).

The duration of overall CR is measured from the time measurement criteria are first met for CR until the first date that progressive disease is objectively documented.

Duration of stable disease: Stable disease is measured from the start of the treatment until the criteria for progression are met, taking as reference the smallest measurements recorded since the treatment started, including the baseline measurements.

11.1.6 Progression-Free Survival

PFS is defined as the duration of time from start of treatment to time of progression or death of any cause.

12. DATA REPORTING / REGULATORY REQUIREMENTS

Adverse event lists, guidelines, and instructions for AE reporting can be found in Section 7.0 (Adverse Events: List and Reporting Requirements).

12.1 Data Reporting

12.1.1 Method

This study will be monitored by the Clinical Data Update System (CDUS) version 3.0. Cumulative CDUS data will be submitted quarterly to CTEP by electronic means. Reports are due January 31, April 30, July 31, and October 31. Instructions for submitting data using the CDUS can be found on the CTEP web site (<http://ctep.cancer.gov>). **Note:** All adverse events that have occurred on the study, including those reported through CTEP-AERS, must be reported via CDUS.

12.1.2 Responsibility for Data Submission

Study participants are responsible for submitting CDUS data and/or data forms to either the Coordinating Center or to the Lead Organization on the study quarterly. The date for submission to the Coordinating Center or to the Lead Organization will be set by them. CDUS does not accept data submissions from the participants on the study. When setting the dates, allow time for Coordinating Center compilation, Principal Investigator review, and timely submission to CTEP by the quarterly deadlines (see Section 12.1.1). For trials monitored by CTMS, a quarterly report of data will be provided by Theradex to the Coordinating Center.

The Coordinating Center is responsible for compiling and submitting CDUS data to CTEP for all participants and for providing the data to the Principal Investigator for review.

12.2 CTEP Multicenter Guidelines

This protocol will adhere to the policies and requirements of the CTEP Multicenter Guidelines. The specific responsibilities of the Principal Investigator and the Coordinating Center (Study Coordinator) and the procedures for auditing are presented in Appendix B.

- *The Principal Investigator/Coordinating Center is responsible for distributing all IND Action Letters or Safety Reports received from CTEP to all participating institutions for submission to their individual IRBs for action as required.*
- *Except in very unusual circumstances, each participating institution will order DCTD-supplied agents directly from CTEP. Agents may be ordered by a participating site only after the initial IRB approval for the site has been forwarded by the Coordinating Center to the CTEP PIO ([contact]) except for Group studies.*

12.3 Collaborative Agreements Language

The agent(s) supplied by CTEP, DCTD, NCI used in this protocol is/are provided to the NCI under a Collaborative Agreement (CRADA, CTA, CSA) between the Pharmaceutical Company(ies) (hereinafter referred to as “Collaborator(s)”) and the NCI Division of Cancer Treatment and Diagnosis. Therefore, the following obligations/guidelines, in addition to the provisions in the “Intellectual Property Option to Collaborator” (http://ctep.cancer.gov/industryCollaborations2/intellectual_property.htm) contained within the terms of award, apply to the use of the Agent(s) in this study:

1. Agent(s) may not be used for any purpose outside the scope of this protocol, nor can Agent(s) be transferred or licensed to any party not participating in the clinical study. Collaborator(s) data for Agent(s) are confidential and proprietary to Collaborator(s) and shall be maintained as such by the investigators. The protocol documents for studies utilizing Agents contain confidential information and should not be shared or distributed without the permission of the NCI. If a copy of this protocol is requested by a patient or patient’s family member participating on the study, the individual should sign a confidentiality agreement. A suitable model agreement can be downloaded from: <http://ctep.cancer.gov>.
2. For a clinical protocol where there is an investigational Agent used in combination with (an)other Agent(s), each the subject of different Collaborative Agreements, the access to and use of data by each Collaborator shall be as follows (data pertaining to such combination use shall hereinafter be referred to as "Multi-Party Data"):
 - a. NCI will provide all Collaborators with prior written notice regarding the existence and nature of any agreements governing their collaboration with

NCI, the design of the proposed combination protocol, and the existence of any obligations that would tend to restrict NCI's participation in the proposed combination protocol.

- b. Each Collaborator shall agree to permit use of the Multi-Party Data from the clinical trial by any other Collaborator solely to the extent necessary to allow said other Collaborator to develop, obtain regulatory approval or commercialize its own Agent.
 - c. Any Collaborator having the right to use the Multi-Party Data from these trials must agree in writing prior to the commencement of the trials that it will use the Multi-Party Data solely for development, regulatory approval, and commercialization of its own Agent.
3. Clinical Trial Data and Results and Raw Data developed under a Collaborative Agreement will be made available to Collaborator(s), the NCI, and the FDA, as appropriate and unless additional disclosure is required by law or court order as described in the IP Option to Collaborator (http://ctep.cancer.gov/industryCollaborations2/intellectual_property.htm). Additionally, all Clinical Data and Results and Raw Data will be collected, used and disclosed consistent with all applicable federal statutes and regulations for the protection of human subjects, including, if applicable, the *Standards for Privacy of Individually Identifiable Health Information* set forth in 45 C.F.R. Part 164.
 4. When a Collaborator wishes to initiate a data request, the request should first be sent to the NCI, who will then notify the appropriate investigators (Group Chair for Cooperative Group studies, or PI for other studies) of Collaborator's wish to contact them.
 5. Any data provided to Collaborator(s) for Phase 3 studies must be in accordance with the guidelines and policies of the responsible Data Monitoring Committee (DMC), if there is a DMC for this clinical trial.
 6. Any manuscripts reporting the results of this clinical trial must be provided to CTEP by the Group office for Cooperative Group studies or by the principal investigator for non-Cooperative Group studies for immediate delivery to Collaborator(s) for advisory review and comment prior to submission for publication. Collaborator(s) will have 30 days from the date of receipt for review. Collaborator shall have the right to request that publication be delayed for up to an additional 30 days in order to ensure that Collaborator's confidential and proprietary data, in addition to Collaborator(s)'s intellectual property rights, are protected. Copies of abstracts must be provided to CTEP for forwarding to Collaborator(s) for courtesy review as soon as possible and preferably at least three (3) days prior to submission, but in any case, prior to presentation at the meeting or publication in the proceedings. Press releases and other media presentations must also be forwarded to CTEP prior to release. Copies of any manuscript, abstract and/or press release/ media presentation should be sent to:

Email: [contact]

The Regulatory Affairs Branch will then distribute them to Collaborator(s). No publication, manuscript or other form of public disclosure shall contain any of Collaborator's confidential/ proprietary information.

13. STATISTICAL CONSIDERATIONS

13.1 Study Design/Endpoints

We are targeting two patient populations based on distinct clinical needs:

This trial will enroll patients who are cetuximab naïve (palliative setting). Typically patients will have been treated with cytotoxic chemotherapy in the first line setting and would be considered for cetuximab single agent therapy. Such patients will be randomized between cetuximab and the combination of ARQ 197 (tivantinib) /cetuximab. This patient population would be analogous to the patient population that was used in the two c-MET inhibitor NSCLC studies that met their primary endpoints (ARQ 197 (tivantinib) ([Sequist et al](#))/ MetMab ([Spigel et al](#))).

Patients who have failed treatment with cetuximab as part of the control arm have the option to receive tivantinib as a single agent. This patient population generally has a very poor prognosis and effective therapies are lacking. Patients who have failed EGFR based therapy (in the recurrent / metastatic setting) typically have a progression-free survival of only 1.8 months (based on data from a historical phase II network study cohort – [DeSouza et al, Clinical Cancer Research, 2012](#)). Such patients have either primary or secondary (acquired) EGFR resistance. We hypothesize based on pre-clinical evidence that c-MET signaling (analogous to data for NSCLC) serves as an “exit” pathway and is a key component in mediating EGFR resistance.

Primary Endpoint: Response Rate

We will compare in the cetuximab/ ARQ 197 (tivantinib) combination with single agent activity of cetuximab..

Secondary Endpoints/Analyses:

a) Continuous tumor shrinkage

b) PFS

c) OS

d) Endpoints a), b), and c) above, as well as response rates, will be assessed and compared between treatment arms in the subgroup of patients with high c-MET expression (anticipated to be ~84% of patients ([Seiwert et al, Cancer Research,](#)

2009), and/or high c-MET copy number (anticipated >10% and largely overlapping with MET IHC (*Seiwert et al, Cancer Research, 2009*)).

e) Single agent activity of ARQ 197 (tivantinib) after failure of cetuximab (descriptive)

13.2 Sample Size/Accrual Rate

We expect to jointly enroll 3-6 patients per month for a total of 76 response evaluable patients (38 patients in each arm) over a period of 18-24 months. Patients will then be followed for at least 6 months.

Comparison of combination arm with single agent cetuximab: Response rates in the two arms will be compared using a continuity-corrected chisquare test. A sample size of n=38 patients per arm will provide 80% power to detect a difference of 12% vs. 35% between the cetuximab and combination treatment arms, using a one-sided test at the alpha=0.10 significance level.

Effect Size: We are assuming a comparably large effect size based on the following rationale:

- Preclinical data suggests high expression levels of MET and EGFR (higher than e.g. for NSCLC) as well as strong synergy for combined inhibition (see above).
- The relatively poor response rate for cetuximab alone (10-13%) masks that many more patients (40%) experience SD and oftentimes experience minor tumor shrinkage. By improving inhibition of an EGFR parallel pathway and achieving synergistic tumor inhibition we expect a substantial proportion of SD assessments to convert to responses.
- The response rates for cytotoxic chemotherapies are generally in this range and it is appropriate that an effective targeted therapy (with most head and neck SCCs expressing both relevant targets) would be similarly effective.
- As a secondary outcome measure we will evaluate continuous tumor shrinkage, which will increase power and allow us to detect a smaller difference.
- Furthermore as a secondary outcome we will evaluate PFS. We are not adequately powered to use PFS as a primary outcome given the sample size limitation. Nevertheless a PFS trend/signal comparable to NSCLC data would provide support to consider further evaluation in a follow-up study and the design would be straightforward given the data from this study to pick the optimal treatment and clinical setting.

Early evaluation for toxicity: For safety evaluation we have scheduled an interim safety evaluation after treatment of 3 and 6 patients with the combination of ARQ 197 (tivantinib) /cetuximab. If less than 2 of 6 patients experience severe toxicities / “DLTs”, the trial will continue, although we will continue to monitor adverse events per standard AE evaluation and reporting guidelines.

Early evaluation for futility:

An interim look for futility will be performed at the time when half of the patients (14 per arm) have been randomized and evaluated for response. If the observed response rate in the combination arm is no higher than in the single agent group, early termination will be considered. This will result in a small power loss of < 2% (*Weiland and Therneau, Cont Clin Trials, 1987*).

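### The futility look is set at 14 per arm and called half, but half of 38 is 19; at 14 the rule costs about 4.3 points of power, not under 2, and leaves the trial below 80%.

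*Combined protocol and SAP*

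**What the plan says.** Section 13.2 (Sample Size/Accrual Rate) plans enrolment "for a total of 76 response evaluable patients (38 patients in each arm"). Section 13.6 repeats the target of 76 evaluable patients. On the primary comparison, 13.2 states: "Response rates in the two arms will be compared using a continuity-corrected chisquare test". It adds: "A sample size of n=38 patients per arm will provide 80% power to detect a difference of 12% vs. 35"%, one-sided at alpha 0.10.

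Under the sub-heading on early evaluation for futility, one interim look is "performed at the time when half of the patients (14 per arm) have been randomized and evaluated for response". Early termination is to be considered if the observed combination response rate is no higher than the cetuximab rate. The paragraph ends on the cost: "This will result in a small power loss of < 2"%, citing a methods paper on two-stage randomized designs with binary outcomes.

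**The concern.** The paragraph gives three facts about the look: it comes at half the patients, it comes at 14 per arm, and it costs less than 2% power. In a trial of 38 per arm the first two cannot both be true. Fourteen is half of 28, and no section gives 28 per arm as the sample size.

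The difference matters because the rule also triggers on ties. With 14 patients per arm and a 12% control rate, small equal counts are common even when the combination works, so an earlier look flags an active combination noticeably more often.

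This is the plan's only efficacy go/no-go before the final analysis. As written, it supports two triggers, 28 or 38 evaluable patients. Randomization is not blinded (13.6), so an ambiguous trigger also leaves room to choose the timing after responses are known.

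**Working it through.** **Inputs, all from 13.2.** Control rate 0.12, combination rate 0.35, difference d = 0.23; one-sided alpha 0.10 (z = 1.2816); power 0.80 (z = 0.8416); continuity-corrected test; 38 per arm; stopping condition: combination responders ≤ control responders.

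**Step 1: reproduce the plan's sample size.** The mean rate is 0.235.

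- Uncorrected: n′ = [1.2816·√(2·0.235·0.765) + 0.8416·√(0.12·0.88 + 0.35·0.65)]² / 0.23² = (0.7684 + 0.4857)² / 0.0529 = 29.7.
- With continuity correction: n = (n′/4)·[1 + √(1 + 4/(n′·d))]² = 37.93, so 38 per arm.

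The plan's 38 is confirmed. Fixed-sample power at 38 is 80.1% by the corrected normal approximation and 81.6% by exact binomial enumeration.

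**Step 2: timing.** 38/2 = 19 per arm, 38 in total. The plan's 14 per arm is 28 in total, and 28/76 = 36.8%.

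**Step 3: power with the look.** Let the look be at m per arm, with X control and Y combination responders at that point. The trial continues only if Y > X; it then adds 38 − m per arm and applies the corrected test to the totals. Hence:

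- P(stop) = Σ over y ≤ x of Bin(x; m, 0.12)·Bin(y; m, 0.35)
- Power = Σ over y > x of Bin(x; m, 0.12)·Bin(y; m, 0.35)·P(final test rejects, given x and y)
- Loss = 81.6% minus that power

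| Look (per arm) | P(stop), 12% vs 35% | Power | Loss (points) | P(stop), 12% in both arms |
|---|---|---|---|---|
| none | – | 81.6% | – | – |
| 14 | 10.2% | 77.3% | 4.3 | 61.8% |
| 18 | 6.8% | 79.7% | 1.9 | – |
| 19 | 6.1% | 80.1% | 1.5 | 60.1% |

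The loss first drops below 2 points at 18 per arm. Two million simulated trials give losses of 4.29 points at 14 and 1.53 at 19. A one-sided Fisher test gives the same 4.3 and 1.5.

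**Step 4: the part played by ties.** At 14 per arm, a strictly lower combination rate has probability 4.15% and a tie 10.23 − 4.15 = 6.08%, so ties make up most of the stopping probability.

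**Step 5: sensitivity to method.** A bivariate normal approximation (correlation √(14/38) = 0.607, continuity correction in the final test) gives 80.1% → 77.7% at 14, a loss of 2.4 points, and 80.1% → 79.3% at 19, a loss of 0.8.

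Reading the plan's 2% as a relative loss does not help. At 14 it is 4.30/81.63 = 5.3% exact, or 2.36/80.07 = 2.9% approximate. At 19 it is 1.51/81.63 = 1.8% exact.

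**The case against.** **Stopping is only to be considered.** The 4.3 points therefore apply only if every trigger leads to termination; if the investigators sometimes continue, the loss is smaller. This stands as a condition. The plan's own figure needs the same condition, so the comparison is like for like.

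**The size depends on method and on ties.** The plan's 80% at 38 per arm comes from the normal approximation, on which the loss at 14 is 2.4 points, not far above 2. If only a strictly lower rate stopped the trial, the exact loss at 14 would be 1.25 points and power 80.4%. The first part stands as a range, but both ends exceed 2 points and leave power below 80%. The second is not the written rule.

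**The 80% is a fixed-sample statement.** It is attached to n = 38 and the final test, and it is correct there; the futility paragraph separately admits some loss. That is fair. But 80% less a loss below 2 points promises more than 78%, and 77.3% or 77.7% does not meet it.

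**The earlier look has merits.** With 12% in both arms it stops about as often (62% vs 60%) and 10 patients sooner. If the rule is always followed, expected evaluable enrolment is 0.618·28 + 0.382·76 ≈ 46 with a look at 14 per arm and 0.601·38 + 0.399·76 ≈ 53 at 19. This is a genuine trade-off. It could justify choosing 14, but not calling 14 half or quoting a loss below 2%.

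**Which number is the slip is not shown.** A 28-per-arm trial with a look at 14 would lose 1.5 points, so 14 may belong to another design; the documents do not say so. That design would have only 67.8% power with the planned test.

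**Conclusion.** The concern holds. The interim timing contradicts itself, and the stated power loss is wrong for a look at 14 per arm. Assuming 12% vs 35%, the corrected test, ties counted and the rule followed whenever it triggers, the loss is 4.3 points (exact) and power is 77.3%; the normal approximation gives 2.4 points and 77.7%. About 1 in 10 trials of a combination with exactly the targeted effect would meet the stopping condition, against about 1 in 16 with a look at 19.

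At 19 per arm, half is right and the loss is below 2 points by either method. Power is 80.1% exact, or 79.3% by the approximation. That makes 19 the likelier intention, though the text does not prove it. The final sample size and test are unaffected, and a futility-only look does not inflate type I error.

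**What to change.** Replace 14 per arm with 19 per arm in the futility paragraph of 13.2, and state the trigger as a count: response assessed in 19 patients per arm, 38 of the planned 76. The words about half and the stated loss can then stay.

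If 14 per arm is intended, delete the reference to half, say that the look comes at 28 of 76 patients (37%), and restate the loss as about 4 points and overall power as about 77%, naming the calculation method.

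In either case, say that ties meet the condition and that the quoted loss assumes the rule is followed. Make the change before the look is taken.

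The amendment is one number. Moving to 19 delays the look by 10 evaluable patients, roughly 10/6 = 1.7 to 10/3 = 3.3 months at the planned 3 to 6 per month. If both arms respond at 12%, it adds about 7 evaluable patients on average.
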